**STUDY SUMMARY**

Study Title	Sedentary time in individuals with ischaemic heart disease and its association with cardiac function, structure and cardiovascular risk factors.
Internal ref. no. (or short title)	Sedentary time and cardiovascular risk factors in IHD
Study Design	Cross-sectional
Study Participants	Ischaemic heart disease patients
Planned Size of Sample (if applicable)	67
Follow up duration (if applicable)	7 days
Planned Study Period	7 days
Research Question/Aim(s)	What is the sedentary pattern of individuals with ischaemic heart disease and its association with cardiac function and cardiovascular risk factors?

**ROLE OF STUDY SPONSOR AND FUNDER**

The Sponsor of this study is the University of Bedfordshire. The sponsor is responsible for the overall conduct and management of the study

There is no external funder for this study.

**ROLES AND RESPONSIBILITIES OF STUDY MANAGEMENT COMMITTEES/GROUPS & INDIVIDUALS**

**Cardiac Rehabilitation Team at Bedford Hospital**

Regular meetings will be held between the Bedford Hospital Cardiac Rehabilitation team and the study investigators to discuss how to conduct the study in terms of participant recruitment, data collection and dissemination.

Sedentary time and IHD

**KEY WORDS:**

Ischaemic heart disease (IHD), Coronary artery bypass graft (CABG), Post- myocardial infarction (post-MI), Cardiac Rehabilitation (CR), sedentary behavior, cardiometabolic risk

Sedentary time and IHD

## STUDY PROTOCOL

### 1 BACKGROUND

Cardiovascular Disease (CVD) is the leading cause of mortality and morbidity globally (World Health Organization, 2019). In the UK alone, it was accountable for 124,641 deaths in 2017. Further to this, CVD contributes to a vast economic burden, costing the National Health Service (NHS) £19 billion annually. This is mainly due to a significant number of hospital readmissions following a first cardiac event (198,000 per annum) (British Heart Foundation, 2018).

Cardiac Rehabilitation (CR) is a secondary preventative measure to further cardiac events. The British Association of Cardiovascular Prevention and Rehabilitation (BACPR) defines CR as 'the coordinated sum of activities required to influence favourably the underlying cause of cardiovascular disease, as well as to provide the best possible physical, mental and social conditions, so that the patients may, by their own efforts, preserve or resume optimal functioning in their community and through improved health behaviour, slow or reverse progression of disease'. It is suggested by the National Institute for Health and Care Excellence (NICE) that all patients should be offered a CR programme with an exercise component following an MI (BACPR., 2017). There is conflicting evidence regarding the benefits of exercise-based CR upon cardiovascular mortality and morbidity, hospital readmissions and all-cause mortality. Previously, CR has been shown to be beneficial in longer term health outcomes of cardiac patients. The 2016 Cochrane Review of Exercise based CR found that, when compared with a no exercise control group, exercise-based CR accounts for an estimated risk reduction of 26% and 18% for cardiovascular mortality and hospital admissions respectively, but no reduction in total mortality or further cardiovascular events (Anderson et al., 2016). Despite BACPR recommending reducing sedentary behaviour following a cardiac event, there is scarce evidence regarding the association of sedentary behaviour with cardiovascular risk or cardiac related outcomes in this population group (Freene et al., 2022).

Sedentary behaviour is defined as a waking energy expenditure of  $\leq 1.5$  METs (metabolic task equivalent) while in a seated, reclined or lying posture (Tremblay et al., 2017).. Due to technological advancements and changes in social norms and workplace behaviours, many population groups engage in high amounts of sedentary behaviour. For instance, in 1377 older men in the UK, self-reported data showed an average of 317 minutes per day of TV viewing, reading, commuting and car use {Jefferis, 2016 #265546}. Further to this, accelerometer derived findings within this study reported an average of 619 minutes per day of sedentary time in older men (Parsons et al., 2016). An international study of 49,493 participants from 20 countries across the world reported a median of 300 minutes per day of sitting (Bauman et al., 2011). However, studies using self-report methods are limited as individuals typically underestimate their sitting time. This may underestimate the true magnitude of association

## Sedentary time and IHD

between sitting time and cardiovascular risk markers. A comparison study of a self-reported questionnaire (international physical activity questionnaire (IPAQ)) and an activPAL accelerometer upon sitting time confirms this, where the IPAQ was found to underestimate sitting time by 3.4 hours per day (Chastin et al., 2014). Hence, estimating sitting using device-based methods is important in contributing to knowledge regarding associations with health outcomes (Celis-Morales et al., 2012).

Sedentary behaviour is associated with cardiovascular risk markers in the general population. Within the US National Health and Nutrition Examination Survey (NHANES) survey, a detrimental linear association was found between total time spent sedentary and waist circumference, high density lipoprotein cholesterol (HDL-C), triglycerides, insulin, insulin sensitivity and  $\beta$  cell function (Healy et al., 2011). In addition, independent of total sitting time, a higher number of breaks in sitting per day was significantly beneficially associated with waist circumference, C-reactive protein and fasting plasma glucose (Healy et al., 2011). Therefore, both reducing total sedentary time and frequently breaking up prolonged periods of sedentary time are associated with improved cardiometabolic risk in the general population (Healy, et al., 2011). Further to this, a meta-analysis which reviewed the association between sedentary behaviour and blood pressure (BP) had somewhat varied findings (Lee & Wong, 2015). Of the 31 articles included, 18 articles found no association between sedentary behaviour and either systolic blood pressure (SBP) or diastolic blood pressure (DBP). Typically, those that did not find a significant association between SB and BP had a smaller sample size, and SB was objectively measured. Despite this, the subsequent meta-analysis (n=28) showed a significant association between SB and BP, of which every additional hour of SB per day was associated with an increase in 0.06 mmHg for SBP and 0.20 mmHg for DBP with an odds ratio of 1.02 (95% CI 1.00-1.03, p=0.02) for high blood pressure (both SBP and DBP). All studies adjusted for confounding variables, including age and sex, but some studies adjusted for more confounders than others (Lee & Wong, 2015). It is important to note that null findings were more prominent in studies that adjusted for moderate to vigorous physical activity, a historically known influence upon BP (Pescatello et al., 2004). However, these studies have typically been conducted in the general population, healthy individuals, or those who are overweight/ obese. There are currently limited studies that investigate the associations of sitting with cardiovascular risk factors in a population who have ischaemic heart disease. Furthermore, there appear to be no studies that have investigated the association of sitting time with cardiac function in this group, which is important to inform the potential importance of targeting reductions in sedentary behaviour as part of cardiac rehabilitation. Therefore, the aim of this study is to determine the prevalence of device measured sitting and the association of sitting with cardiovascular risk factors and cardiac function in individuals who have ischaemic heart disease.

Sedentary time and IHD

#### **4 RESEARCH QUESTION/AIM(S)**

- 1) How much time do individuals with ischaemic heart disease spend sitting per day?
- 2) What is the association of daily sitting with cardiac function, structure and cardiovascular risk factors in ischaemic heart disease?

##### **4.1 Objectives**

- 1) To identify daily sitting time in individuals with ischaemic heart disease in the first year of their cardiac recovery.
- 2) To establish objective associations of sitting time with cardiac function, structure and cardiovascular risk factors, including anxiety and depression.

#### **5 STUDY DESIGN and METHODS of DATA COLLECTION AND DATA ANALYSIS**

##### Study protocol

An observational, cross-sectional study design will be used. Participants can have preliminary measures taken either during a visit to the Sport and Exercise Sciences Laboratories at the University of Bedfordshire or in their own home, depending on the participant's preference. This consists of anthropometric measures (height, weight and waist circumference). Participants will then rest for 5 minutes to achieve a steady state before baseline blood pressure is taken. Baseline cardiac function measures will be measured using an echocardiogram scan, as well as an electrocardiogram (ECG) to ensure there are no electrical contraindications to the heart (including new ST depression / elevation or any arrhythmias) which would make the participant unsuitable to complete the study. Mood and wellbeing measures will then be assessed using questionnaires.

Following this, participants will be asked to complete 7 full days of normal daily activity, whilst wearing an activPAL monitor on their thigh to record sitting, standing and stepping. The main data collection will take place at the participant's home, workplace or leisure setting (i.e. under free-living conditions), with social distancing in place if required at the time of data collection. Instructions will be given to help ensure that the 7-day monitoring period reflects their usual habits. The monitoring period will also be carefully decided, to ensure it does not conflict with any events that are out of the usual for the participant, such as holidays or work-based events, which would alter their usual sedentary patterns.

##### Data collection

##### *Demographic data*

### Sedentary time and IHD

Patient demographic data will include age, gender, diagnosis and intervention. This is routinely collected within Cardiac Rehabilitation as part of their usual standard of care.

### *Height and weight*

Equipment to measure height, weight and waist circumference will include a stadiometer (Leicester Height Scale, Marsden HM-250P, Leicester, UK) to measure height in cm, a measurement tape for waist circumference and digital weighing scales (Tanita, BWB0800, Allied Weighing, UK) to measure weight in kg.

### *Blood pressure and heart rate*

Blood pressure and heart rate will be measured in an upright, seated position using an automated device (Omron M5-1 automated oscillatory device, Omron Matsusaka Co. Ltd., Matsusaka, Japan). The left arm will be used to measure blood pressure unless there is preference for the right arm due to any potential previous medical conditions. Two measures will be taken, with 5 minutes apart.

### *Cardiac function*

In a laboratory or in the participants home, the participant will be asked to undress from the waist up and lay on the medical couch in the left lateral decubitus position. Here, a scanning gel will be applied to the echocardiogram probe. This forms part of the echocardiogram system (Esoate, MyLab Omega, Italy). Parasternal and apical views will be acquired (Armstrong and Ryan., 2012). Once these images are collected and stored, the gel will be removed from the probe and chest. All images will be stored anonymously, where participants will be given a participant ID number. All image analysis will be completed using Echopac software (GE Healthcare, Version 113, GE healthcare, Chicago, Illinois, United States). Measures taken from the echocardiogram scan will be used to calculate left ventricular structure and function.

### *Anxiety and Depression*

The Hospital Anxiety and Depression Scale {Zigmond, 1983 #285206} will be used to assess feelings of anxiety or depression.

### *Measurement of sitting, standing and light physical activity*

## Sedentary time and IHD

Following preliminary measures, sitting, standing and stepping will be monitored 24 h/day over seven full days using an activPAL activity monitor (PAL Technologies, Glasco, Scotland). This will measure changes in posture and level of activity by cadence. The activity monitor will be attached to the skin with a waterproof dressing on the anterior right thigh. The Processing PAL application will be used to process the data collected from the activPAL device. It uses a validated algorithm to isolate waking and sleeping time and to generate the outcome data. Participants will also be given a 7 day activity diary to record waking times, and other relevant activities to cross-validate the Processing PAL measured sleep and wake times.

### **Data analyses**

Statistical analyses will be conducted using SPSS Version 28 (IBM, Armonk, NY, USA). Descriptive statistics will be reported as mean and standard deviation (SD). Data will be checked for normality across each category using quantile-quantile plots. Total sitting time, breaks in sitting, standing and light, moderate and vigorous intensity physical activity, and total number of sit to stand transitions (frequency of breaks) data will be presented as mean and SD and also expressed as a percentage of daily waking time.

Correlation coefficients will be used to explore relationships of sedentary time variables with cardiac and cardiovascular risk factors. Multiple regression analysis will be used to model each aforementioned independent variable separately with cardiovascular risk factors (blood pressure, BMI, waist circumference, anxiety and depression) and measures of cardiac function and structure. It will also be used to explore associations between sedentary time with cardiovascular risk factors and cardiac function and structure, adjusting for potential confounding variables, including type of condition, time since diagnosis of cardiac condition, age, gender, ethnicity, and socioeconomic status, and whether any measures are confounding variables to the association between sedentary time with cardiovascular risk factors and cardiac function and structure.

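### Breaks in sitting are modelled separately, with no stated adjustment for total sitting time; an added exploratory model would separate break frequency from sitting volume (minor)

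*Protocol*

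**What the plan says.** The Data analyses text in Section 5 lists the activity variables: "Total sitting time, breaks in sitting, standing and light, moderate and vigorous intensity physical activity, and total number of sit to stand transitions (frequency of". The bracket, cut short here, labels the transitions as a measure of break frequency. The text then states that "Multiple regression analysis will be used to model each aforementioned independent variable separately with cardiovascular risk factors" and with measures of cardiac function and structure.

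The next sentence turns to sedentary time and its associations, "adjusting for potential confounding variables, including type of condition, time since diagnosis of cardiac condition, age, gender, ethnicity, and socioeconomic status". It also provides for exploring "whether any measures are confounding variables to the association between sedentary time with cardiovascular risk factors and cardiac function and structure". Total sitting time is not named as a covariate for any other exposure.

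Section 1 (Background) reports from an earlier general-population survey that, "independent of total sitting time, a higher number of breaks in sitting per day was significantly beneficially associated" with several risk markers. It concludes that "both reducing total sedentary time and frequently breaking up prolonged periods of sedentary time are associated with improved cardiometabolic risk" in the general population. The Study Summary asks about the sedentary pattern of these patients and its associations. The association objective in Section 4.1 is narrower: "To establish objective associations of sitting time with cardiac function, structure and cardiovascular risk factors, including anxiety and depression".

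**The concern.** Breaks and total sitting time are two descriptions of the same days, so they may be correlated. If they are, a breaks model without sitting time gives a coefficient that mixes how often sitting is interrupted with how much sitting there is. That coefficient cannot be set beside the Background result, which was obtained independently of total sitting time. It also gives only a partial answer to the sedentary-pattern question in the Study Summary.

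What is at stake is interpretation. If the separate coefficient is reported as showing that breaks matter in their own right, it could mislead in either direction, depending on the sign of the breaks-sitting correlation. If it is reported as an overall association, it does not mislead.

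Two wording matters lie in the same sentence. Breaks in sitting and sit-to-stand transitions appear as separate items without a statement of how they differ. The text also says that "transitions (frequency of breaks) data will be presented as mean and SD and also expressed as a percentage of daily waking time", although a count of transitions has no share of waking time.

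**Working it through.** **Inputs.** From Section 7.2.1: n = 67, planning correlation r = 0.3 between sedentary time and cardiac outcomes, 80% power, alpha 5%. From Section 5: six named covariates. Assumed, because the protocol gives no value: breaks-sitting correlation ρ with absolute value 0.1, 0.3, 0.5 or 0.7. Also assumed: standardised normal variables, and no effect of breaks once sitting is held fixed.

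**The plan's own figure.** An exact correlation test at r = 0.3 needs 67 participants one-sided (power 0.803) and 84 two-sided (power at 67 is 0.704). So 67 reproduces as a one-sided calculation. Sidedness is a separate matter; the illustration below uses two-sided 5% tests.

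**What the separate model estimates.** Leaving sitting out gives an expected breaks coefficient of β_breaks + β_sitting × ρ. With β_breaks = 0 and β_sitting = 0.3, this is 0.3 × ρ: 0.03, 0.09, 0.15 and 0.21 SD. At ρ = −0.3 it is −0.09.

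**How often it would be significant.** By Fisher z with no other covariates, the test statistic is centred at atanh(0.3ρ) × √(67 − 3) = 8 × atanh(0.3ρ).
- At ρ = 0.3: 8 × 0.0902 = 0.722. P(Z > 1.96 − 0.722) + P(Z < −1.96 − 0.722) = 0.108 + 0.004, about 0.11.
- At ρ = 0.7: 8 × 0.2132 = 1.705. P(Z > 0.255) is about 0.40, and the other tail is negligible.

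Simulation (16,000 studies per cell) agrees and adds the case with six further independent covariates:

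| Assumed size of ρ | Expected coefficient (SD) | Significant, no other covariates | Significant, six covariates |
|---|---|---|---|
| 0.1 | 0.03 | 5.8% | 5.5% |
| 0.3 | 0.09 | 11.1% | 10.4% |
| 0.5 | 0.15 | 22.5% | 20.9% |
| 0.7 | 0.21 | 40.0% | 37.4% |

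With sitting time in the model, the breaks term is significant in 4.6% to 5.3% of studies. With six covariates and sitting left out, a sitting-outcome correlation of 0.2 gives 5.3%, 7.5%, 12.1% and 18.5%; a correlation of 0.4 gives 6.1%, 15.8%, 34.4% and 60.9%.

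**Precision cost of adding sitting time.** The ratio of standard errors (with / without) is approximately √[0.91 / ((1 − 0.09ρ²)(1 − ρ²))] × √(60/59). Here 0.91 = 1 − 0.3², and 60 = 67 − 7 and 59 = 67 − 8 are the degrees of freedom left for the breaks variable after the intercept and the six covariates, without and with sitting.
- ρ = 0.3: √(0.91 / (0.9919 × 0.91)) × 1.008 = 1.01
- ρ = 0.5: √(0.91 / (0.9775 × 0.75)) × 1.008 = 1.12
- ρ = 0.7: √(0.91 / (0.9559 × 0.51)) × 1.008 = 1.38

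**Degrees of freedom.** If each covariate takes one term, the residual is 67 − (1 + 6 + 1) = 59, falling to 58 with sitting added. Section 7.1.1 names post-infarction (two types), post-bypass and post-percutaneous-intervention patients, so type of condition alone has three or four groups and takes two or three terms. That gives 58 to 57, or 57 to 56, and fewer still if ethnicity and socioeconomic status are coded as categories.

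**The case against.** The strongest reply is that no stated aim fails. The research questions in Section 4 and the objectives in Section 4.1 concern sitting time. The Background result on breaks belongs to an earlier study, and its conclusion is limited to the general population. The same section ends with this study's own aim, which does not mention breaks. The covariate list is open, and the exact covariates of a supporting model are commonly left to an analysis plan, which is not shown here. The separate model estimates a valid quantity. In the illustration the overall association of breaks is truly non-zero, so the significant results are correct detections of that association; they are false positives only under an independent-effect reading.

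Most of this stands, and it is why the point is minor. A reader might infer that the protocol rules out adjustment for sitting time, or that it cannot address breaks beyond volume at all. The text supports neither, since its list is open and it allows other measures to be examined as confounders. Those clauses are, however, written for sedentary time as the exposure, and they follow an explicit statement that each variable is modelled separately. They therefore do not settle what the breaks models contain. A reader might also infer that the two break items are one measure listed twice. The text does not settle that either: only the transitions item is labelled as break frequency, so the other could be a different quantity, such as a duration.

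**Conclusion.** The point holds as a minor, low-cost improvement, not as an error in a stated objective. As written, the breaks models give an overall association and do not on their own separate break frequency from sitting volume. That distinction is the one on which the Background motivates breaks, and it bears on the sedentary-pattern question in the Study Summary. The analysis of sitting time itself is unaffected.

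The size is unknown and rests on the assumed breaks-sitting correlation. At absolute correlations up to 0.3 the effect is small (about 11% significant against a nominal 5%). At 0.7 it is large (about 40%, or 37% with six covariates). Both figures assume a sitting-outcome correlation of 0.3 and no independent effect of breaks.

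**What to change.** Keep the separate breaks model. Add an exploratory model with the same covariates plus total sitting time, and report the two side by side. Base any statement that breaks matter independently of sitting volume on the adjusted model only. State whether the named covariates apply to the breaks models. Ask the sponsor to say whether breaks in sitting and sit-to-stand transitions are the same measure, and to define each if they are not. Limit the percentage of waking time to time variables.

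This takes a few sentences and no new data. The costs are:
- One more model term. At an assumed partial correlation of 0.3 with six single-term covariates, two-sided power goes from 0.661 to 0.654 before any collinearity.
- A larger standard error for breaks if the two exposures are correlated: about +1%, +12% or +38% at absolute correlations of 0.3, 0.5 or 0.7.
- A second set of breaks tests across blood pressure, BMI, waist circumference, anxiety, depression and the echocardiographic measures, to be labelled exploratory.
- If breaking up sitting also lowers total sitting, the adjusted model leaves that pathway out, which is why both models should be shown.

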## **7 SAMPLE AND RECRUITMENT**

### **7.1 Eligibility Criteria**

#### **7.1.1 Inclusion criteria**

- Patients diagnosed with *ischemic heart disease* within the past 12 months (within National Audit of Cardiac Rehabilitation (NACR) outcome data). This includes post myocardial infarction (ST wave elevated MI or Non-ST wave elevated MI), post coronary artery bypass graft, post percutaneous coronary intervention.

